4.3.3. Safety Set

The Safety Set will include all participants who received any IP. All analyses using the Safety Set will group participants according to the study vaccine actually received.

The Safety Set will be used for safety and demography analyses.

5. Participant Disposition

5.1. Disposition

Participant disposition will be summarized by dose group for all participants. A disposition of participants includes the number and percentage of participants for the following categories: participants who were enrolled, who were vaccinated, participants who discontinued from the study (i.e., did not complete the Day 180 visit), and participants who were in the Enrolled Set, PP Set and Safety Set.

A participant may withdraw or be withdrawn from the study for any of the following reasons:

• The participant does not meet the protocol inclusion or exclusion criteria

- The participant is noncompliant with the protocol
- The participant has a serious or intolerable AE(s) that in the investigator's opinion requires withdrawal from the study
- The participant has safety laboratory results that reveal clinically significant hematological or biochemical changes from the baseline values, per investigator judgment
- The participant has symptoms or an intercurrent illness not consistent with the protocol requirements or that justify withdrawal
- The participant is lost to follow-up
- Other reasons (e.g., pregnancy, development of contraindications of use of the IP)
- The participant withdraws consent, or the investigator or sponsor decides to discontinue their participation in the study withdrawal of consent by participant or the investigator or sponsor decides to discontinue their participation in the study.

Participant status summaries will also be provided that include participants who completed each visit, participants vaccinated with study vaccine, participants who had immunogenicity results at an applicable visit, and participants who completed the study. Participant status summary will be also presented by dose and age group.

Participant disposition and discontinuation data will be presented in a listing sorted by age, dose group and participant number.

The number of participants included in each analysis set will be summarized. A listing of participants in each analysis set will also be provided by age, dose group and participant number. Participants excluded from the analysis sets will be listed with reason for exclusion(s) and sorted by age, dose group and participant number.

The primary reasons for study discontinuation include:

- AE,
- Death,
- Lost To Follow-up,
- Physician Decision,
- Pregnancy,
- Protocol Deviation,
- Site Terminated by Sponsor,
- Study Terminated by Sponsor,
- Withdrawal of Consent by Participant,

- Vaccine Not Administered,
- Other.

5.2. Protocol Deviations

Major protocol deviations are a subset of protocol deviations that may significantly impact the completeness, accuracy, or reliability of the study data or that may significantly affect a participant's rights, safety, or well-being. Major protocol deviations rules will be developed and finalized before database lock.

Major protocol deviations include, but are not limited to, the following:

- Study vaccine not administered at all
- Invalid/missing informed consent
- Fraudulent data
- Administration of concomitant vaccine(s) forbidden in the protocol
- Participants got vaccinated but not as per protocol
- Vaccine storage temperature deviation which is not accepted by quality
- Expired vaccine administered
- Ineligible participant
- Administration of any medication forbidden by the protocol
- Participants did not comply with blood sample schedule
- Serological results not available pre- or post-vaccination for at least neutralizing Abs against pseudovirus bearing S protein from
- Serological results available but results unreliable (e.g. wrong blood sample management)

The number of participants with major protocol deviations will be summarized by dose group. Major protocol deviations will be listed with date of occurrence, deviation description, and analysis set from which participant is excluded. The major protocol deviation summary will be based on the Safety Set.

The major protocol deviations will be listed by age group, dose group, participant number and will be reported in the CSR.

6. Demographics and Baseline Characteristics

6.1. Demographics

A summary of demographics and baseline information will be presented by dose group. The demographic characteristics consist of age (years), gender at birth, ethnicity, and race. The

baseline characteristics consist of height (cm), weight (kg), BMI (kg/m²), N protein, and prior Covid-19 infection, defined as either self-reported Covid-19 infection or a positive N protein result from the last result/test prior to vaccination.

Descriptive statistics (mean, standard deviation, median, minimum and maximum) for age, height, weight and BMI will be provided by dose group in each age group and overall.

The number and percentage of participants will be provided for gender at birth, ethnicity, race, baseline RT PCR, prior Covid-19 infection and baseline N protein status by dose group in each age group and overall.

Percentages will be based on the total number of participants in the analysis set defined in the output.

Participant demographic and baseline characteristics will be sorted by age group, dose group and participant number, including child-bearing potential (applicable only for women).

6.2. Baseline Disease Characteristics

Not applicable

6.3. Medical History

6.3.1. General Medical History

Medical history will be coded using the latest version of the Medical Dictionary for Regulatory Activities (MedDRA). The number and percentage of participants with any medical history, medical history that ended before Visit 1, and medical history that is still ongoing at Visit 1(at the time of first vaccination) will be summarized overall and for each system organ class (SOC) and preferred term (PT) by dose group. Percentages will be calculated based on safety set.

Participant medical history data including specific details will be presented in a listing sorted by age group, dose group and participant number.

6.4. Inclusion and Exclusion Criteria

Enrolled participants who failed any inclusion/met any exclusion criteria will be classed as major protocol deviations.

7. Treatments and Medications

7.1. Prior and Concomitant Medications

All medications/vaccination will be coded according to the World Health Organization (WHO) drug dictionary (WHODrug), which will be updated whenever available throughout the study.

7.1.1. Prior Medications

Any medications (including vaccines) that were administered to the participant within 6 months of Screening (within 18 months for prior vaccines) will be considered as prior medication for this study.

Prior medication will be listed sorted by age group, dose group, participant number and summarized by dose groups using the Safety Set. They will be summarized by the generic preferred name and anatomical therapeutic chemical (ATC) class level 4. More than one ATC class per medication is possible and the medication will be reported under all applicable classes. A participant with multiple occurrences within an ATC is counted only once for that ATC class. Similarly, a participant with multiple occurrences within a generic preferred name is counted only once.

7.1.2. Concomitant Medications

Concomitant medications are defined as any medications and vaccine (other than study vaccines) taken after the first dose of the study vaccine that were taken:

- Within 6 months of Screening or
- First prior to the dosing and on-going after first dose up to 6 months or
- Within 2 weeks of study vaccination for herbal products, vitamins, minerals, and overthe-counter medications.

Concomitant medications will be listed and summarized in a similar manner to that of prior medications.

For the purpose of inclusion in prior and concomitant medications tables, incomplete start and stop dates will be imputed according to the below rules (where UK, UKN, and UNKN indicate unknown or missing day, month, and year, respectively):

Missing Start Dates

If day is missing and month and year are available:

• UK-MMM-YYYY: Assume 01-MMM-YYYY (first day of the month), but if month and year are the same as the first study vaccination month and year, then assume the date of first vaccination.

If day and month are missing and year is available:

• UK-UKN-YYYY: Assume 01-JAN-YYYY (first day of the year), but if year is the same as the first study vaccination year, then assume the date of first study vaccination.

If day, month and year (date) are missing:

• UK-UKN-UNKN: Assume date of first study vaccination.

Missing Stop Dates

If day missing and month and year are available:

• UK-MMM-YYYY: Assume the last day of the month

If day and month are missing and year is available:

• UK-UKN-YYYY: Assume 31-DEC-YYYY

if day, month and year (date) are missing:

• UK-UKN-UNKN: Do not impute and assume ongoing

(Note - In case of single dose vaccine or treatment, start date may be same as that of end date.)

7.2. Study Treatments

7.2.1. Extent of Exposure and Compliance

A listing of vaccine exposure will be provided. The listing will include assigned study vaccine, actual vaccine received, date and time of the vaccination and sorted by age group, dose group and participant number.

8. Analysis of Safety and Immunogenicity Study Objectives

8.1. Analysis of Primary Safety Objective

8.1.1. Analysis of Medically attended Adverse Events (MAAEs), Serious Adverse Events (SAEs), and Adverse Events of Special Interest (AESIs) from study vaccination through the end of the study (Day 1 – 180)

Participants' MAAEs and SAEs from study vaccination through the end of the study (approximately 180 days after the study vaccine administration, day 1-180) will be presented as the percentage of participants with such events throughout the study duration by dose and age group. Participant's AESIs from study vaccination through the end of the study (day 1-180) will be presented by dose group.

8.1.2. Analysis of solicited local and systemic adverse events up to 7 days after study vaccination (day 1-7), unsolicited adverse events, abnormal laboratory findings up to 28 days after study vaccination (day 1- 28) and non-serious Covid-19 adverse events (Day 1 – study end)

The percentage of participants with at least one solicited local or systemic AE for 7 days following vaccination (day 1-7), participants with unsolicited AEs up to 28 days after study vaccination (day 1-28), participants with abnormal laboratory findings up to 28 days after study

vaccination (day 1-28) and non-serious Covid-19 adverse events (day 1 – study end) will be computed by dose group.

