8.4. Analysis of COVID -19 Incidence-Adverse Event of Special Interest

Proportion of participants with the following will be summarized by dose group:

- 1. Laboratory-confirmed (RT PCR) symptomatic SARS-CoV-2 infection
- 2. Laboratory-confirmed asymptomatic or symptomatic (RT-PCR or N protein seroconversion) SARS-CoV-2 infection
- 3. Laboratory-confirmed severe SARS CoV-2 infection
- 4. Medically attended visits due to laboratory-confirmed SARS-CoV-2 infection
- 5. Hospitalizations or death due to laboratory-confirmed SARS-CoV-2 infection

Frequencies and estimates of the proportion of participants with the above events from study vaccination through the end of the study will be computed by dose group.

9. Safety Analysis

Safety, tolerability, and reactogenicity will be assessed by clinical review of all relevant parameters including solicited and unsolicited AEs, SAEs, AESIs, MAAEs, AEs leading to withdrawal from study participation, safety laboratory test results, vital signs, and physical examination findings.

All safety analyses will be based on Safety Set. All safety analyses will be provided by dose group and age group unless otherwise specified.

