9.1. Adverse Events

An AE is defined as any untoward medical occurrence in a participant enrolled into this study regardless of its causal relationship to the IP. This definition includes exacerbations of preexisting conditions. Stable pre-existing conditions which do not change in nature or severity during the study are not considered AEs; however, these should be reported as part of the medical history at screening.

SOC will be displayed in alphabetical order. PT will also be displayed alphabetically within SOC. Percentages will be based upon the number of participants in the Safety Set within each dose group.

Incomplete AE onset date/time and end date will be imputed following the rules below.

Missing Start Dates

If day is missing and month and year are available:

• UK-MMM-YYYY: Assume 01-MMM-YYYY (first day of the month), but if month and year are the same as the first study vaccination month and year, then assume the date of first vaccination.

If day and month are missing and year is available:

• UK-UKN-YYYY: Assume 01-JAN-YYYY (first day of the year), but if year is the same as the first study vaccination year, then assume the date of first study vaccination.

If day, month and year (date) are missing:

• UK-UKN-UNKN: Assume date of first study vaccination.

Missing Stop Dates

If day missing and month and year are available:

• UK-MMM-YYYY: Assume the last day of the month

If day and month are missing and year is available:

• UK-UKN-YYYY: Assume 31-DEC-YYYY

if day, month and year (date) are missing:

• UK-UKN-UNKN: Do not impute and assume ongoing

All AEs will be classified by SOC and PT according to the latest version of the MedDRA.

Unless otherwise specified, AEs will be summarized by dose group based on the Safety Set. A listing of AEs will be provided by age group, dose group and participant number. All events from screening until vaccination will be considered as medical history.

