9.1.6. Adverse Events of Special Interest

An AESI (serious or nonserious) is defined as an AE or SAE of scientific and medical concern specific to the sponsor's product or program, for which ongoing monitoring and rapid communication by the investigator to the sponsor could be appropriate (ICH E2F; CIOMS VI). Adverse events of special interest will include the following events:

- Virologically-confirmed SARS-CoV-2 infections (see protocol Section 6.6 for disease definitions)
- Potential immune-mediated disorders (see protocol Section 13.4 for definitions)
- Anaphylaxis or severe hypersensitivity within 24 hours after study vaccine administration
- Pericarditis or myocarditis

AESIs will be identified using MedDRA queries and Investigator identification as per eCRF. Refer to appendix 15.3 for details on these queries.

The percentage of participants with AESIs with onset date within day 1-28 and within day 1-180, identified by either the investigator or by MedDRA queries will be provided by SOC and PT for each dose group.

Similarly, AESIs that are related to COVID-19 will be presented in a separate listing by age group, dose group and participant number.

AESIs will be reported until exit from study (up to day 180 after the study vaccine administration, Day 1-180).

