9.1.7. Serious Adverse Events

An SAE is defined as any event that:

- Results in death
- Is immediately life-threatening
- Requires inpatient hospitalization or prolongation of existing hospitalization
- Results in persistent or significant disability/incapacity
- Is a congenital anomaly/birth defect
- Is an important medical event that may not result in death, be life-threatening, or require hospitalization but, based upon appropriate medical judgment, jeopardizes the participant or may require medical or surgical intervention to prevent one of the other outcomes listed in this definition. Examples of such medical events include allergic bronchospasm requiring intensive treatment in an emergency room or at home, blood dyscrasias or convulsions that do not result in inpatient hospitalization, or the development of drug dependency or drug abuse.

The percentage of participants with SAEs onset date within day 1-180 will be provided by dose group, by grade, outcome and causality.

The number and percentage of participants with SAE onset date within day 1-28 and within day 1-180 will be summarized by SOC, PT and causality for each dose group (any, fatal, causally related, fatal/causally related).

SAEs will be summarized and listed from the time participant signs the ICF until exit from study (up to day 180 after the study vaccine administration, day 1-180).

A data listing for all SAEs will be provided by age group, dose group and participant number.

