9.1.8. Medically Attended Adverse Events

Medically attended adverse events (MAAEs) is defined as an AE that results in a visit to a medical professional. Medically attended visits are defined as telemedicine visit, physician's office visit, urgent care visit, emergency room visit, hospitalization, or death. Scheduled study visits will not be considered medically attended visits. Medically attended adverse events related

to study vaccination are to be reported from the time of first study vaccination until completion of the participant's last study-related procedure, which may include contact for safety follow-up.

The percentage of participants with MAAE onset date within day 1-180 will be provided by dose group and by grade.

All MAAEs and treatment-related MAAEs with onset date within day 1-28 and within day 1-180 will be presented in separate summary tables for each dose and age group and total by SOC and PT. All MAAEs will be presented in a data listing by age group, dose group and participant number.

MAAEs will be reported in both listings and summaries from the time participant signs the ICF until exit from study (up to day 180 after the study vaccine administration, day 1-180).

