9.5. Electrocardiogram

Not applicable.

10. Pharmacokinetics

Not applicable.

11. Pharmacodynamics

Not applicable.

12. Interim Analysis

A first interim analysis of safety and immunogenicity data covering at least neutralizing Ab titers against pseudovirus bearing S protein from ^{CCL} up to 14 days after study vaccine administration in participants enrolled in Cohorts 1, 2, and 3 will be performed including at least day 1 and day 15 data. A second interim analysis of safety and immunogenicity data covering at least neutralizing Ab titers against pseudovirus bearing S protein from ^{CCL} was planned, however this was cancelled as the study was closed early.

13. Changes in the Planned Analysis

Not applicable.

14. References

Department of Health and Human Services (DHHS), Food and Drug Administration, Center for Biologics Evaluation and Research (US). Guidance for industry. Toxicity grading scale for healthy adult and adolescent volunteers enrolled in preventative vaccine clinical trials. September 2007 [cited 2021 Jul 09]. Available from: https://www.fda.gov/media/73679/download

World Health Organization (WHO). WHO coronavirus (COVID-19) dashboard [Internet]. 2021 [cited 2021 Jul 07]. Available from: https://covid19.who.int/

15. Appendices

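### The study was closed early, yet Day 1-180 safety and COVID-19 results are planned only as crude percentages; if follow-up was shortened unequally by dose, they are not comparable across doses

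*SAP*

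**What the plan says.** The first primary endpoint, in protocol section 2 and SAP 2.1, is the percentage of participants with MAAEs, SAEs and AESIs from vaccination to about Day 180.

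- **MAAEs and SAEs.** SAP 8.1.1 says that these "will be presented as the percentage of participants with such events throughout the study duration by dose and age group".
- **AESIs.** SAP 9.1.6 plans "The percentage of participants with AESIs with onset date within day 1-28 and within day 1-180".
- **COVID-19.** SAP 8.4 says that the "proportion of participants with the above events from study vaccination through the end of the study will be computed by dose group". It names no denominator of its own.
- **Denominator for AEs.** SAP 9.1: "Percentages will be based upon the number of participants in the Safety Set within each dose group".

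On closure, SAP section 12 says that the second interim analysis "was planned, however this was cancelled as the study was closed early". It gives no date, does not list the doses reached and does not say what happened to participants still on study. SAP section 13 records no change to the planned analysis. Protocol 4.2.2 has the investigator withdraw participants if the sponsor terminates the study, and SAP 5.1 lists termination by the sponsor among the discontinuation reasons.

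**The concern.** A crude percentage over a 180-day window is a fair estimate of 180-day risk only if everyone is observed for 180 days or until an event. The plan has no rule for participants who are not. They stay in the denominator, and their unobserved days count as event-free.

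This matters because dose is tied to calendar time. Participants enter by dose cohort in sequence, and Cohorts 4 and 5 wait for Day 1 to 8 data from all participants in the previous cohorts. A calendar cut-off would then leave later cohorts with fewer days of observation. The endpoint is meant to describe safety at each dose level, so a difference in time on study could be read as a difference between doses.

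Nothing else in the visible plan deals with this. Protocol 7.6 leaves missing safety data to the SAP, which supplies only imputation of partial dates (SAP 9.1). SAP 7.2.1 plans a listing of vaccine exposure. There is no person-time rate, time-to-event estimate or summary of follow-up duration.

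**Working it through.** **1. The plan's own figures.** SAP 4.1 gives n = 30 per dose group and the chance of seeing at least one AE, 1 - (1 - p)^30.
- p = 5%: 1 - 0.95^30 = 78.5%, as stated.
- p = 10%: 1 - 0.90^30 = 95.8%, as stated.

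Both figures take p as the incidence over the whole window in which the participant is observed.

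**2. Effect of shorter follow-up on a crude percentage.** Inputs that I assume, because the documents give neither: 180-day risks R of 10%, 20% and 30%, and follow-up f of 120, 90 or 60 days for every member of a group. With a constant hazard, the daily rate is -ln(1 - R)/180, and the crude percentage expected by day f is 1 - (1 - R)^(f/180).

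For R = 20%: 1 - 0.80^(120/180) = 13.8% and 1 - 0.80^(90/180) = 10.6%.

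| True 180-day risk | 180 days | 120 days | 90 days | 60 days |
|---|---|---|---|---|
| 10% | 10.0% | 6.8% | 5.1% | 3.5% |
| 20% | 20.0% | 13.8% | 10.6% | 7.2% |
| 30% | 30.0% | 21.2% | 16.3% | 11.2% |

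If only half of a group stopped at Day 90 and the rest reached Day 180, a true 20% would show as (20.0 + 10.6)/2 = 15.3%.

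**3. Follow-up-adjusted measure.** Under the same hazard, events per person-time do not depend on f. For R = 20% the rate is 100 × 365.25 × (-ln 0.80)/180 = 45.3 per 100 person-years at every follow-up length. For 10% and 30% it is 21.4 and 72.4.

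**4. Detection.** If the 5% of SAP 4.1 is read as a 180-day incidence, the incidence by Day 90 is 1 - 0.95^(90/180) = 2.53%. The chance of at least one event in 30 is then 1 - (1 - 0.0253)^30 = 53.7%, against 78.5%. At 120 and 60 days it is 64.2% and 40.1%.

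**5. Against sampling error.** The exact 95% interval is 7.7% to 38.6% for 6/30 and 2.1% to 26.5% for 3/30. A fall from 20% to about 10% lies within the noise of one dose group. The shift is systematic, however, and adds to that noise.

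**The case against.** The strongest objection is that no passage says that any vaccinated participant was followed for less than 180 days. The closure is mentioned only to explain a cancelled interim analysis, and that interim was tied to Cohorts 4 and 5 (protocol 3.1 and 7.7). The wording fits equally well with escalation having stopped while everyone already vaccinated was followed to Day 180. A listed discontinuation reason does not show that anyone was discontinued for it. This stands, and it makes the point conditional.

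A reader might also infer that the highest doses will look safer because they were observed for less time. The documents do not support that. They do not say which doses were given. The 2 and 4 µg groups are randomized together (SAP 4.2), and Cohorts 2 and 3 open after data from three sentinels of the previous cohort, so enrolment from 2 to 12 µg can overlap. For COVID-19, incidence changes with calendar time, so the bias could go either way.

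The plan is not blind to incomplete follow-up. SAP 5.1 counts by dose group "participants who discontinued from the study (i.e., did not complete the Day 180 visit", and summarizes visit completion by dose and age group. Fixed 28-day tables are planned too. For SAEs, "The number and percentage of participants with SAE onset date within day 1-28 and within day 1-180 will be summarized by SOC"; for MAAEs, "All MAAEs and treatment-related MAAEs with onset date within day 1-28 and within day 1-180 will be presented in separate summary tables"; AESIs have the same two windows. The other two primary endpoints end by Day 7 and Day 28. This also stands: a careful reader of the report would see an imbalance in completion and would have early-window results to compare. Neither corrects the Day 1-180 percentages.

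Finally, the endpoint is defined as a percentage in a descriptive study without hypothesis tests. That is a reason to keep the crude figures, and it does not prevent adding others beside them.

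**Conclusion.** The point holds as a conditional gap in the analysis. The Day 1-180 percentages for MAAEs, SAEs, AESIs and COVID-19 take no account of time on study, in a plan that itself records early closure of a trial enrolled by dose in sequence. If closure or drop-out shortened follow-up unequally, these percentages are not comparable across doses. If everyone reached Day 180, they are sound.

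The size is unknown. The illustration (20% showing as 13.8% or 10.6%) rests on a constant hazard, assumed risks and a whole group stopping at the same day. If events cluster soon after vaccination, the loss is smaller. It would be wrong to conclude that follow-up was in fact truncated, or that a dose relation was hidden or reversed: the documents show neither.

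**What to change.** 1. In SAP sections 12 and 13, state the closure date, the dose groups reached, and whether any participant's follow-up was cut short.
2. Beside the completion counts of SAP 5.1, report median follow-up and total person-time by dose group.
3. In SAP 8.1.1, 8.4 and 9.1.6 to 9.1.8, keep the crude percentages as the defined endpoint. For Day 1-180, add the Kaplan-Meier cumulative percentage at Day 180 with 95% CI, censoring at last contact, and events per person-time with exact CI.
4. Where any dose group has incomplete follow-up, rest statements that compare doses at Day 180 on the follow-up-adjusted estimates. If nobody in a group reaches Day 180 while still at risk, say that its Kaplan-Meier value there cannot be estimated, and note that the person-time rate assumes a roughly constant hazard.
5. For COVID-19, note that neither estimate removes confounding by calendar time.

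The cost is SAP wording and a few extra tables from onset and last-contact dates, with no new data collection. The added estimates will be imprecise at 30 per dose group.
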